## **7 STATISTICAL ANALYSIS**

The statistical analysis of the primary, secondary and safety endpoints is to be understood in the exploratory sense. No confirmatory hypothesis testing is planned.

The described analyses will be done if the number of patients is appropriate. Especially for the combination of age group and the subpopulations described in section 5.1 a frequency analysis may be replaced by a listing of the relevant data.

The efficacy analysis for the primary endpoint will be performed with the data from the first bleeding event of each patient using the FirstBLEED analysis set (ITT analysis) as the primary population and using the FirstBLEED-PP analysis set (PP analysis) as a secondary population. An additional analysis will be performed for all bleeding events on the BLEED and BLEED-PP population. The primary analysis population for the PK analysis will be the PK-PP population.

Please refer to section 13 for an overview of tables (marked “T”), listings (“L”) and figures (“F”).

### **7.1 Summary Tables**

All collected efficacy and safety assessments will be presented by means of descriptive statistics. If not detailed otherwise, the parameters listed below will be tabulated according to the different types of data. The number of subjects in the analysis population (N) and the number of subjects contributing to each particular summary (n) will be included in every presentation.

- Binary data (whether or not an event has occurred): counts and proportions
- Count data (the frequency of an event in a set time period): rate (count per unit time)
- Continuous data (measurements on a continuous scale, including quasi-continuous variables): arithmetic mean, standard deviation, median, minimum, maximum
- Scales data (Ordinal and Non-ordinal): absolute and relative frequencies

Additional descriptive and exploratory statistics, such as confidence intervals, are included as appropriate. If not mentioned otherwise, confidence intervals are to be understood as two-sided, 95% confidence intervals.

### **7.2 Figures**

Figures will always reference the number of subjects contained in the analysis population and the number of observations represented in the graphic. Various types of graphs, including bar charts, scatter plots, line plots, and plots showing means and standard deviations will be used to illustrate the statistical outcome.

### **7.3 Listings**

Listings for the display of individual data summarized in tables and figures will be provided.

### **7.4 Interim Analysis**

An administrative interim analysis will be performed after at least 12 patients have undergone PK assessment within the study. The interim analysis will focus on the PK data only (Chapter 14: Tables 14.2.24-14.31, selected tables of 14.1, and related listings and graphs). The results of the interim analysis will have no impact on the further conduct of the study. There will be no additional SAP for the interim analysis.

### **7.5 Methods for Handling Missing Data**

In general missing data values will not be replaced, except for the following:

- Body weight: In case of missing weight, the last available weight measurement will be used for calculation of the pharmacokinetic parameters in the PK phase of the study and recovery investigations (last observation carried forward).
- For the handling of missing FIX levels with regard to the PK analysis see Chapters 6.1 (PK-PP) and 6.2 (Major Protocol Deviations).

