Physical examination		x										x
Vital signs	x					x		x	x			x
TEE questionnaire	x		x	x	x	x	x	x	x	x	x	x
Body weight	x											
Blood draw for:												
Fibrinogen activity		x [a,b,c]		x [a,b,c]	x [b,c]	x [b,c]	x* [b,c]	x [b,c]	x [b,c]	x* [b,c]	x [b,c]	
Fibrinogen antigen		x [a,c]		x [a,c]	x [c]	x [c]	x [c]	x [c]	x [c]	x [c]	x [c]	
Safety lab (haematology and clinical chemistry) [b]		x			x			x				
Infusion of Octafibrin		x	x**				x [e]			x [e]		
Haemostatic efficacy assessments (intra- and postoperative)				x [f]							x [g]	
Wound haematomas and oozing					x				x			
Narrative of outcome												x
AEs [h]		>	>	>	>	>	>	>	>	>	>	
Concomitant medications		>	>	>	>	>	>	>	>	>	>	
Medical history since last study visit												x

TEE = thromboembolic event; AE = adverse event; POP = postoperative.

\* ≤ 30 minutes before each infusion of Octafibrin.

\*\* If considered necessary.

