#### **9.2.9 SURG population**

The SURG population will include all surgical interventions with a need for at least one infusion of the IMP during the time period from the day of surgery until overall clinical assessment of haemostatic efficacy (third inclusion criterion; see Section 4.2) in subjects of the FAS.

A SURG-PP population comprising surgical interventions with no major protocol deviations will be defined in the SAP with criteria similar to the FirstBLEED-PP population.

**NOTE:** Any protocol deviations which will lead to the exclusion from an analysis population other than those mentioned above must be agreed upon in writing by the Sponsor and the study statistician, and in any case, before database closure.

The efficacy analysis for the primary endpoint will be performed with the data from the first bleeding event of each patient using the FirstBLEED population (ITT analysis) as the primary population and using the FirstBLEED-PP population (PP analysis) as a secondary population. An additional analysis will be performed for all bleeding events on the BLEED and BLEED-PP population. The primary analysis population for the PK analysis will be the PK-PP population.

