## 9.6 Handling of Missing Data

In general, if not stated differently, missing data will not be imputed.

If the haemostatic efficacy assessment is missing, it will be set to ‘none’ in the ITT analysis. Subjects with missing haemostatic efficacy assessment will be excluded from the PP population.

Missing PK parameters, MCF and IVR values will not be replaced.

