Surgery analysis set (SURG): all documented surgical interventions with a need for at least one infusion of the IMP during the time period from the day of surgery until day of overall clinical assessment of post-operative efficacy in subjects of the FAS.

Surgery per protocol analysis set (SURG-PP): all surgeries of the SURG analysis set, where the patients underwent the surgery fulfil the following conditions:

- Provide valid, i.e., non-missing, intra- and post-operative efficacy data for the surgery
- Received  $\geq 90\%$  of the planned total dose of the IMP in the first infusion prior to the surgery
- Received  $\geq 80\%$  of the calculated dose (if no dose was calculated, 0% will be assumed) of the IMP over all further infusions of the surgery according to the treatment schedule
- Did not meet any of the following exclusion criteria:
  - Bleeding disorder other than congenital fibrinogen deficiency
  - End-stage liver disease (i.e., Child-Pugh-score B or C)
  - Suspicion of an anti-fibrinogen inhibitor as indicated by previous IVR, if available  $<0.5 \text{ (mg/dL)/(mg/kg)}$
  - Treatment with any fibrinogen concentrate or other fibrinogen-containing blood product within 2 weeks prior to start of treatment for the bleeding episode.

- Did not use any coagulation-active drug (i.e., non-steroidal anti-inflammatory drugs, warfarin, coumarin derivatives, platelet aggregation inhibitors) within 1 week prior to start of treatment for the first bleeding episode, or as a planned or expected medication during the time period from Day 1 until 24 hours (i.e., 1 day) after the last *Octafibrin* infusion

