### 10.1 Treatment of first bleeding episode

The first bleeding episode covers the time period from the first *Octafibrin* infusion until 24 hours (i.e., 1 day) after the last infusion or the end of the treatment observation period, whichever comes last

Haemostatic efficacy will be displayed by covariates (sex, age groups, weight, and type of bleeding) in tables or with covariates in listings depending on the number per subgroup.

The following will be presented following the manners of presentation described in section 7:

- Number of subjects with at least one bleeding episode
- Type of first bleeding episode (spontaneous, traumatic, post-operative, other)
- Site of first bleeding episode
- The duration of the first bleeding episode will be calculated.  
If the end time of a bleeding episode is missing it will be set to 23:59 of the same day, if the start time of a bleeding episode is missing it will be set to 0:00 of the same day.
- Severity of the first bleeding episodes (mild, moderate, severe)
- Efficacy assessment of the treatment made by the investigator (excellent, good, moderate, none) for the first bleeding episode.

For the following subjects, the haemostatic efficacy outcome will be set to the worst efficacy category, i.e., 'none':

- Subjects who withdraw from the study due to lack of efficacy during or after the first bleeding episode
- Subjects receiving cryoprecipitate or concentrates containing fibrinogen other than the IMP between first infusion and efficacy assessment for the first bleeding episode (unless it is clearly documented that these products were administered for reasons unrelated to IMP efficacy [e.g., pharmacy error])
- Subjects with missing haemostatic efficacy assessment after the first bleeding episode
- In addition to the four points scale the proportion of first bleeding episodes successfully treated with *Octafibrin* will be evaluated. "Successfully treated" are all "excellent" and "good" efficacy ratings of treated bleeding episodes. A two-sided 95% CI for the success rate in haemostatic efficacy ('excellent' or 'good') according to Clopper/Pearson will be computed.
- Treatment details: number of exposure days, number of injections, dosing incl. batch numbers., consumption of *Octafibrin* (IU/kg) for the first bleeding episode will be listed

- Any haemostatic co-medication will be listed.

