#### 10.4 Efficacy of Octafibrin in all Bleeding Episodes

The same analyses as described for the first bleeding episode will be done for the total number of bleeding episodes.

Haemostatic efficacy will be displayed by covariates (sex, age groups, weight, and type of bleeding) in tables or with covariates in listings depending on the number of bleeding episodes per subgroup.

The following will be presented following the manners of presentation described in section 7:

- Type of bleeding episodes (spontaneous, traumatic, post-operative, other)
- Site of bleeding episodes
- duration of bleeding episodes

If the end time of a bleeding episode is missing it will be set to 23:59 of the same day, if the start time of a bleeding episode is missing it will be set to 0:00 of the same day.

- Severity of bleeding episodes (mild, moderate, severe)
- Efficacy assessment of the treatment of a bleeding episode made by the investigator (excellent, good, moderate, none)

In the following situations the haemostatic efficacy outcome will be set to the worst efficacy category, i.e., 'none':

- Subjects who withdraw from the study due to lack of efficacy: all bleeding episodes of that subject
- Subjects receiving cryoprecipitate or concentrates containing fibrinogen other than the IMP between first infusion and efficacy assessment (unless it is clearly documented that these products were administered for reasons unrelated to IMP efficacy [e.g., pharmacy error]): the actual bleeding episode
- Subjects with missing haemostatic efficacy assessment: the actual bleeding episode
- In addition to the four point scale the proportion of bleeding episodes successfully treated with *Octafibrin* will be evaluated. "Successfully treated" are all "excellent" and "good" efficacy ratings of treated bleeding episodes. A two-sided 95% CI for the success rate in haemostatic efficacy ('excellent' or 'good') according to Clopper/Pearson will be computed.
- The final efficacy assessment of each patient will be adjudicated by an Independent Data Monitoring & Endpoint Adjudication Committee (IDMEAC). The results of the adjudication will be shown together with the assessments of the investigator.

- Treatment details: number of exposure days, number of injections, dosing incl. batch numbers., consumption of *Octafibrin* (IU/kg per month, per year, per bleeding episode) will be listed
- Increase and decrease of doses of *Octafibrin* used to treat individual bleeding episodes will be listed.

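### The SAP has no rule for a missing surgical efficacy rating, although Protocol 9.6, on its most natural reading, scores it 'none'; the gap would probably favour the product

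*SAP*

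**What the plan says.** **Protocol 9.6** (Handling of Missing Data): "If the haemostatic efficacy assessment is missing, it will be set to ‘none’ in the ITT analysis". The same section removes such subjects from the per-protocol population.

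**SAP 7.5**: "In general missing data values will not be replaced, except for the following". Two items follow: body weight, carried forward from the last measurement, and a cross-reference for missing FIX levels in the PK analysis. Haemostatic ratings are not listed.

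**SAP 10.1 and 10.4** bring back the 'none' rule for bleeds. The cases scored 'none' include, for the first bleed, "Subjects with missing haemostatic efficacy assessment after the first bleeding episode" and, for all bleeds, "Subjects with missing haemostatic efficacy assessment: the actual bleeding episode".

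**SAP 10.5** (Surgical Prophylaxis) has one imputation rule: ratings after a switch to another FIX product count as 'none'. It says nothing about a missing rating. Neither does Protocol 9.3.2.5.

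**SAP 4.3.6 and Protocol 7.2.2.4** derive surgical success or failure from a 4x4 table of adjudicated intra- and post-operative ratings. The table covers excellent, good, moderate and none, and has no entry for missing.

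**SAP 6.1** makes it a condition for SURG-PP that the case "Provide valid, i.e., non-missing, intra- and post-operative efficacy data for the surgery". The SURG set has no such condition.

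**The concern.** Efficacy in preventing bleeding during and after surgery is a stated secondary objective, and a success/failure result is prespecified for it. A surgery can lack a rating, for instance after withdrawal or early discharge. The protocol appears to have a conservative answer for that case. The SAP drops it from its general missing-data section, restores it for bleeds, and leaves surgery with only the no-replacement default.

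The study is open-label and uncontrolled and may contain as few as two surgeries, so one such case can change the surgical result visibly. If the choice is left until the ratings are known, it is made with the outcome in view, and the easiest option (leaving the case out) is the favourable one.

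**Working it through.** The plan gives no figure to reproduce: no sample size calculation is provided and no confidence interval is specified for surgery. The check is a comparison of texts followed by simple counts.

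**1. Does Protocol 9.6 reach surgical ratings?**

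For the wider reading:
- Both documents use its term for surgical ratings. The protocol's surgical flow chart has a row beginning "Haemostatic efficacy assessments (intra- and postoperative", the title of the 4x4 table in both documents refers to haemostatic efficacy, and SAP 10.5 uses the term in its product-switch rule.
- SURG is drawn from the FAS, which both documents frame on the intention-to-treat principle. Item 14.2.21 in SAP section 14, on the subjects and procedures in the surgery analysis, is labelled for ITT and PP.
- Protocol 9.3.1 already scores a missing first-bleed rating as 'none', and 9.3.2.4 extends that approach to all bleeds. If 9.6 concerned bleeds only, its 'none' sentence would add nothing. This is suggestive, since a missing-data section may simply repeat a rule.
- SURG-PP already applies the other half of 9.6, the per-protocol exclusion. Only the 'none' half is absent.

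For the narrower reading: Protocol 9.2.9 ties the ITT label to bleeds, "using the FirstBLEED population (ITT analysis) as the primary population", and SAP section 7 does the same.

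The wider reading is the more natural one, but it is not explicit.

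**2. What does the SAP do with an unrated surgery?** SURG admits it. SAP 7.5 does not replace the rating, SAP 10.5 has no exception, and the table has no cell for it, so no result is defined. SAP 7.1 reports the number in the population (N) and the number contributing (n), so the likely outcome is that the case counts in N but not in n.

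**3. What happens if the missing rating is set to 'none'?** Reading the table:

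| Other rating | Result with 'none' |
|---|---|
| Excellent | Primary adjudication |
| Good | Failure |
| Moderate | Failure |
| None, or also missing | Failure |

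The result is the same whichever of the two ratings is missing.

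**4. Size.** Assume exactly one unrated surgery among k surgeries, with all others successes.
- Left out: (k − 1)/(k − 1).
- Counted as failure: (k − 1)/k.

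| k | Left out | Counted as failure | Difference |
|---|---|---|---|
| 2 | 1/1 = 100% | 1/2 = 50% | 50 points |
| 4 | 3/3 = 100% | 3/4 = 75% | 25 points |

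Two is the minimum in SAP 4.3.6 and in most of the protocol; four is the number in Protocol 3.1.2.2. If the case goes to primary adjudication and is judged a success, the counts are 2/2 and 4/4, and the percentage does not change.

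**The case against.** A reader might infer four stronger claims. The documents do not support them.

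- **The protocol and SAP contradict each other on surgery.** The protocol's ITT label is explicitly attached only to FirstBLEED, and Protocol 9.3.2.5 has no missing-rating rule of its own. On the narrow reading both documents are silent on surgery and do not disagree. That objection stands against calling it a contradiction. The gap remains on either reading.
- **The SAP removes unrated surgeries.** It never says so. SURG keeps them, and N and n are both shown. The IDMEAC adjudicates all haemostatic results with a review of the surgical case, and might assign an outcome. But no rule says it does this when a rating is missing, so leaving the count is likely, not certain.
- **The SAP replaces nothing except body weight, so the primary endpoint is exposed.** SAP 10.1 and 10.4 replace missing bleed ratings, and also missing bleed start and end times. The primary and all-bleeds endpoints follow the protocol.
- **SURG becomes the same as SURG-PP.** The two would coincide on this one criterion only. SURG-PP also has dose, eligibility and concomitant-drug conditions.

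It is also fair to say that the stakes are modest. All analyses are descriptive, and surgical results may be given as listings; the planned surgical efficacy output (the second item numbered 14.2.23) is one. With two surgeries a reader would see each case. This limits the harm, but the overall success/failure result still has to be assigned. The product-switch rule in SAP 10.5 is no substitute, because it addresses a switch and not a missing rating, and it names FIX products.

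**Conclusion.** The point holds as a gap in the SAP. An unrated surgery in SURG has no defined result, while the protocol's missing-data rule, on its most natural reading, would score the missing rating 'none'. Applying the SAP's default would probably take the case out of the success count, which favours the product.

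The illustrative size is 100% against 50% with two surgeries and 100% against 75% with four. This assumes one unrated surgery, successes elsewhere, and a final result of failure for that case. It shrinks to nothing if primary adjudication turns the case into a success.

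The effect is confined to a descriptive secondary endpoint. It is worth correcting because so few surgeries are planned and the protocol already supplies the principle.

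**What to change.** - **SAP 7.5:** list the haemostatic efficacy assessment, for bleeds and surgeries, as an exception to the no-replacement rule, with references to 10.1, 10.4 and 10.5.
- **SAP 10.5:** state that in the SURG set a missing intra- or post-operative rating is set to 'none' before the success/failure table is applied. 'None' paired with excellent then goes to IDMEAC primary adjudication, and every other pairing is a failure.
- **SAP 10.5:** state that all SURG surgeries stay in the denominator and that, as far as missing ratings are concerned, unrated surgeries are excluded only from SURG-PP.
- Because the table takes adjudicated ratings, say whether 'missing' means that the clinician's rating is absent or that no adjudicated rating exists.

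The cost is a few sentences, to be settled before the surgical ratings are reviewed for analysis. No data collection changes. The surgical success count may come out slightly less favourable.

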### **7.6 Dropouts**

A complete list of dropouts will be presented, including the reason for dropout, the phase of the study (PK or non-PK phase) in which the patient dropped out and the duration of participation in the trial in terms of total days as well as exposure days to *Octafibrin*.

### **7.7 Statistical Analytical Issues**

The statistical analysis of the primary, secondary and safety endpoints is to be understood in the exploratory sense. Therefore no confirmative statistical analysis is planned.

Subgroup analyses are planned for the two age strata (age groups < 6 years and  $\geq 6$  - 12 years) regarding PK results, in treatment of BEs and in surgical procedures as well as regarding adverse events.

## 9 EVALUATION OF TREATMENT COMPLIANCE AND EXPOSURE

Pharmacokinetic assessments including Recovery:

- Schedule of PK assessments and deviations will be listed.
- Total dose and dose per kg body weight administered for PK assessments will be summarized.

Treatment of BEs and treatment during bleedings and surgeries: The following will be tabulated and/or summarized:

- Number of Injections
- Number of Exposure Days
- Total Dose, dose per indication (bleeding event, surgery)
- Doses (IU FIX/kg BW) per indication (bleeding event, surgery)

Furthermore the *Octafibrin* batches used will be listed.

## 10 EVALUATION OF TREATMENT EFFICACY

The primary endpoint is the overall clinical assessment of haemostatic efficacy of *Octafibrin* in treating the first documented bleeding episode of each patient (FirstBLEED population).

The efficacy will be evaluated by descriptive statistics and all results will be presented stratified by the age groups (2-<6 years, 6-12 years), if appropriate, and in total. The stratification will be done according to the age of the patients at the screening assessment and patients will stay in the respective stratum for all analyses even when the age of the patient crosses the border of the first stratum.

Secondary endpoints are the clot strength after treatment of a bleeding episode with *Octafibrin*, the in-vivo recovery, the efficacy of *Octafibrin* in all bleeding episodes, and the surgical prophylaxis.

